Effects of Caffeinated Chewing Gum on Shot Put Performance

Document Date: Jan 05 2026

IRB approved date: August 1, 2025

Project summary

15-20 active throwers who have received professional shot put training are expected to be recruited for the study. In a randomisation crossover design, the study was divided into caffeinated chewing gum trial (CCG) and placebo trail (PL). Participants wore a heart rate monitor to record their heart rate and heart rate variability during the experiment, and were given either a caffeinated chewing gum containing 3 mg/kg of body weight (CAP trial) or a placebo chewing gum, and rested for 15 minutes. After the warm-up, the athletic ability test and shot put performance were conducted in order. Saliva samples were collected for analysis of caffeine and α -amylase before and at the end of the experiment.

Introduction

The shot put is a discipline emphasizing explosive power, requiring athletes to propel the shot to a standard height and angle within a brief timeframe to achieve optimal distance. Previous studies have shown that increased sympathetic nervous system activation can effectively enhance energy output during maximal exercise intensity and improve torque during isometric contraction of the quadriceps femoris. Research on caffeine and shot put performance remains limited. In a 2012 published in 2012, morning caffeine supplementation significantly improved alertness and throwing distance in shot put athletes. Another study found that 3 mg of caffeine per kilogram of body weight effectively enhanced several physiological indicators related to explosive power, but only marginally affected shot put distance. Considering the combined findings of these two studies, current research has not specifically examined the effects of caffeine supplementation on autonomic nervous system changes or blood and saliva biochemical indicators. Therefore, future studies that strengthen the investigation of these two areas would still hold potential for publication.

Methods

Study design

This study employed a randomized crossover, double-blind experimental design, divided into two trials: the caffeinated chewing gum trial (CCG) and a placebo trial (PL). All trials were scheduled for completion during the off-season. Off-season training featured similar schedules Monday through Friday, with weekends reserved for

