rest and recovery. Consequently, trials commenced on Mondays following athletes' return from rest periods to ensure consistent pre-trial recovery states. Following the first trial, after 5 days of rest and 2 days of recovery, the second and third trials will be conducted immediately. The trial sequence will be randomized by computer.

Participants

This study plans to recruit 15-20 active throwing athletes with professional shot put training as subjects. Inclusion criteria are: 1. At least 6 years of training in shot put or related track and field throwing events. 2. No cardiovascular or joint diseases. 3. Recovered from sports injuries such as strains or sprains for at least 3 months. Exclusion criteria are: 1. Non-specialized track and field throwers. 2. Presence of cardiovascular or joint diseases, or any conditions that may be exacerbated by exercise. 3. Female and underage subjects. 4. Individuals with caffeine sensitivity. The consent form is completed after the participant has given consent. This study was conducted following the Declaration of Helsinki.

Protocol

All experiments are scheduled to commence at 3:00 PM. Upon arrival at the assembly area, participants must rest in a seated position for at least 10 minutes. Subsequently, saliva samples will be collected for subsequent biochemical analysis. Concurrently, participants will wear heart rate monitors to record heart rate and heart rate variability changes throughout the experiment. Immediately after, participants chewed caffeine gum (3 mg/kg body weight) for 10 minutes (CCG trial) or caffeine-free placebo gum (3 mg/kg body weight) for 10 minutes (PL trial) before discarding it. They then began a dynamic warm-up lasting approximately 15 minutes. For caffeine gum, chewing for 10 minutes followed by a 15-minute rest period allowed for peak salivary caffeine concentration. Following the warm-up, a second saliva sample was collected. After sample collection, participants sequentially performed maximum grip strength, vertical jump, and squat tests. After testing, subjects rested for 5 minutes before performing the shot put-specific test. Following this test, participants provided another saliva sample, concluding the entire testing protocol.

Caffeine and placebo gum

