The caffeinated chewing gum employed in the present study (Military Energy Gum, Arctic Mint flavour; Stay Alert, Chicago, USA) has been utilised in previous studies(1, 2). It is estimated that a single piece of gum contains approximately 5 grams and 100 milligrams of caffeine. The placebo gum was a commercially available blue mint gum

(Lotte Gum Mint., Ltd., Tokyo, Japan). In order to administer a dose of 3 mg/kg of caffeine per unit of body weight, it was necessary to crush, grind, blend, reshape and flavor all chewing gums with 0.3 g of peppermint-flavored powder. The process was designed to ensure that the new chewing gums were comparable to the original in terms of appearance, color, flavor, weight and size. Previous studies have demonstrated that this method renders it impossible for the participant to distinguish the type of gum (1, 3).

Saliva sample collection and analysis

Saliva samples were stored in a refrigerator at -80 degrees immediately after collection. For analysis, samples were thawed and centrifuged at 4000 rpm for 5 min. 500 μ L of saliva samples were transferred to glass tubes for mass spectrometry analysis and Enzyme-linked immunosorbent assay (ELISA) analysis respectively. The analysis of saliva α -amylase concentration was conducted utilising an enzyme-linked immunosorbent assay (ELISA) with commercially available reagents (Neogen Corporation, Kentucky, USA; Salimetrics LLC, State College, PA, USA).

Statistical analysis

All data are presented as means \pm standard deviations. The Shapiro–Wilk test was utilised to evaluate the normality of the data. The grip strength and number of fall on each rounds between the two trials were analyzed using paired t-tests. The saliva caffeine and α -amylase concentration and RPE were analyzed using two-way ANOVA with repeated measures. If the interaction effect (trial \times time) were significant, the Bonferroni method was used to perform post hoc comparisons. Effect sizes were calculated using Cohen's d to quantify the magnitude of observed effects and defined as trivial (<0.20), small ($0.20\text{--}0.40$), moderate ($0.40\text{--}0.80$), and large (>0.8), respectively. The power value of each data was conducted using G*Power 3.1.9.6 software (4)

Reference

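### Bonferroni is named for the post hoc comparisons of saliva and RPE, where Holm's method gives the same family-wise error control and is never less powerful (minor)

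*Protocol*

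**What the plan says.** The Statistical analysis section assigns salivary caffeine, salivary alpha-amylase and RPE to one model: "concentration and RPE were analyzed using two-way ANOVA with repeated measures". If the trial-by-time interaction is significant, "the Bonferroni method was used to perform post hoc comparisons". It does not say which comparisons are made, how many there are, or at what overall alpha.

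The Protocol subsection of Methods describes three saliva collections per visit:

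- After the seated rest and before any gum: "Subsequently, saliva samples will be collected for subsequent biochemical analysis".
- After chewing and warm-up: "Following the warm-up, a second saliva sample was collected".
- After the shot put test: "participants provided another saliva sample, concluding the entire testing protocol".

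The Project summary describes only two collections, "before and at the end of the experiment". No times are given for RPE anywhere in the document.

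**The concern.** Naming the multiplicity method is a choice that the protocol itself makes, so it can be judged without seeing a separate analysis plan. For any family of two or more comparisons, Holm's step-down procedure gives the same family-wise guarantee as Bonferroni, needs no assumption about how the tests are correlated, and cannot reject fewer hypotheses. With 15 to 20 athletes there is little power to spare. The Introduction gives the lack of work on saliva biochemistry as part of the reason for the study, so alpha-amylase is not an incidental outcome.

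A second, weaker element is the divisor. Until the family is named, the Bonferroni threshold is not determined: two post-gum contrasts, one contrast per sampling time and all pairs of cells each give a different one.

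**Working it through.** The protocol states no power, alpha or planning effect for these outcomes, so there is no figure of its own to reproduce.

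**Inputs from the protocol.** There are two conditions (CCG and PL). The Protocol subsection gives three saliva times, one before the gum and two after. The sample size is 15 to 20, each athlete serving as his own control.

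**Assumptions.** Two-sided family-wise alpha of 0.05 within each outcome. True paired difference d = 0.8 in units of the SD of the within-athlete differences, with other values shown below. Correlation of 0.5 between the two post-gum contrasts. The prior requirement of a significant interaction is ignored.

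**Step 1: possible families.** A 2 × 3 layout has 6 cells and 6 × 5 / 2 = 15 pairs. CCG versus PL at each time gives m = 3, and at the post-gum times only, m = 2. The per-comparison alphas are 0.05/2 = 0.025, 0.05/3 = 0.0167 and 0.05/15 = 0.0033. If the Project summary's two collections were right, the layout would be 2 × 2, with 4 × 3 / 2 = 6 pairs and a single post-gum contrast.

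**Step 2: Bonferroni power per contrast.** For a paired t-test, power = P(|T| > t_crit), where T is noncentral t with n − 1 degrees of freedom and noncentrality d√n, and t_crit is the 1 − 0.05/(2m) quantile of central t. For d = 0.8 the noncentrality is 0.8√15 = 3.10 and 0.8√20 = 3.58.

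| Family | t_crit, n=15 | Power, n=15 | t_crit, n=20 | Power, n=20 |
|---|---|---|---|---|
| m = 2 | 2.51 | 72% | 2.43 | 86% |
| m = 3 | 2.72 | 65% | 2.63 | 82% |
| m = 15 | 3.53 | 38% | 3.35 | 59% |

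Naming two contrasts instead of three therefore adds 72 − 65 = 7 points at n = 15 and 86 − 82 = 4 points at n = 20.

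**Step 3: Holm against Bonferroni for m = 2.** Bonferroni rejects each contrast with p ≤ 0.025. Holm rejects the smaller p-value if it is ≤ 0.025 and, if so, then tests the larger at 0.05. Every Bonferroni rejection is therefore also a Holm rejection. Results from 100,000 simulated trials, both contrasts at 0.8 SD:

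| | Bonferroni | Holm |
|---|---|---|
| Per contrast, n=15 | 72% | 78% |
| Per contrast, n=20 | 86% | 91% |
| Both declared, n=15 | 57% | 70% |
| Both declared, n=20 | 78% | 86% |

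**Step 4: sensitivity.**

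- Correlation: at n = 15, power to declare both is 52% (Bonferroni) and 67% (Holm) at correlation 0, and 63% and 73% at correlation 0.8. The gain does not hinge on the assumed 0.5.
- One real contrast and one null (n = 15, correlation 0.5): 71.7% and 71.9% for the real one, so practically no gain.
- Very large effects: at d = 1.5 and n = 15, Bonferroni with m = 2 already has 99.9% power, so nothing is left to gain.

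**The case against.** **Bonferroni is valid, conventional and gives simple simultaneous confidence intervals, so choosing it is not an error.** This stands. The point is an available improvement, and the gain is conditional: Step 4 shows it vanishing when only one contrast is real or when effects are very large. The latter may be so for salivary caffeine after caffeinated gum (an assumption).

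**The make-up of a post hoc family is commonly left to an analysis plan.** This also stands, and the silence about the family is not itself counted as a fault. The named method is different, because the protocol fixes it.

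**Within-trial change over time may be of interest with serial sampling.** This is fair, and it is why those comparisons are kept as secondary instead of being dropped.

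**A reader might infer more:** that the plan applies Bonferroni to all 15 pairs and so roughly halves the power of the contrasts that matter. The text does not support this. It never says that all pairs are tested, and CCG versus PL at each time fits it equally well. The size also depends on an effect that the protocol does not give. At d = 0.8, a 15-pair family would keep 38/72 = 0.53 of the two-contrast power at n = 15, but 59/86 = 0.69 at n = 20. At d = 1.0 it would keep 0.71 and 0.87.

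**Conclusion.** The point holds as a minor improvement to a stated method. Holm gives the same error control as Bonferroni for any family of two or more comparisons and cannot lose power. The gain is about 5 to 6 points per contrast and 8 to 13 points for declaring both, given two post-gum contrasts truly at 0.8 SD with correlation 0.5. It ranges down to nearly nothing in the cases shown in Step 4, so it matters more for alpha-amylase, and perhaps RPE, than for salivary caffeine.

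The fall to 38% (n = 15) or 59% (n = 20) would arise only if all 15 pairs were tested, which the protocol does not prescribe. The two-contrast layout rests on the three samples of the Protocol subsection. If the Project summary's two were right, there would be one post-gum contrast and Holm and Bonferroni would coincide. Shot put distance is not among the outcomes under this rule, and grip strength has its own paired t-test, so neither is affected.

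**What to change.** In the Statistical analysis section, replace the Bonferroni method with Holm's method, applied within each outcome to CCG versus PL at the post-gum times. For saliva these are the second and third samples of the Protocol subsection. Report within-trial changes over time as secondary. State the times at which RPE is recorded and apply the rule to RPE at those times. Reconcile the Project summary's two saliva collections with the three in the Protocol subsection, since the number of contrasts depends on it.

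The cost is a short text edit, with no change to conduct, sample size or data collected. The one statistical drawback is that confidence intervals matching Holm's procedure are less simple than Bonferroni intervals.
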